6.6 VISIT PROCEDURES

6.6.1 Screening (V1)

Eligibility of participants to participate in this study will be assessed at the screening visit (V1). The ICF will be signed, dated and timed prior to any other screening procedures. At the end of this visit, participants will be given instructions on the use of the messaging and questionnaire system that will be used daily to collect information about smoking status (starting the next day) and IMP compliance (after V2).

The sequence of the following questionnaires and assessments will be at the discretion of the Investigator (or designee) after signature of the ICF. Whenever possible, blood draws should be performed after all other assessments are complete.

6.6.1.1 *Questionnaires*

- Smoking History
- Registration Form
- Medical History (with Review of Systems)

6.6.1.2 *Assessments*

- Review of Prior and Concomitant Medication
- Review of Concomitant Disease and Medical History
- Expired air CO breath test
- Alcohol breath test
- Urine collection for urinalysis and drug screen
- Blood collection for safety laboratory testing (including pregnancy test for all females) and for future biospecimen research (for those participants who consented to this optional collection)
- Vital signs (systolic and diastolic blood pressure, pulse rate, and respiratory rate), will be measured in sitting position after the participant has rested for at least 5 minutes. After two minutes of standing, a second blood pressure reading (systolic and diastolic) and pulse rate will be obtained.
- Height and weight / BMI
- Temperature
- Electrocardiogram (ECG) -- A standard 12-lead ECG will be recorded after the participant has rested for at least 5 minutes in a supine position.
- Columbia-Suicide Severity Rating Scale (C-SSRS)
- Physical examination

6.6.2 Baseline (V2) – Day -1

Visit 2 will occur within 28 days of the screening visit. Participants will come to the Center to complete questionnaires, assessments, and for dispensing of IMP. Participants will begin the study drug regimen the day after V2 (Day 1). Date and time of first dose will be collected via electronic message.

The sequence of the following questionnaires and assessments will be at the discretion of the Investigator (or designee).

6.6.2.1 ***Questionnaires***

- Reasons to Smoke
- Other Nicotine Use Questionnaire
- Modified Cigarette Evaluation Questionnaire Extended (mCEQE)
- Minnesota Withdrawal Questionnaire
- Modified Shiffman-Jarvik Withdrawal Scale
- Fagerström Test for Nicotine Dependence

6.6.2.2 ***Assessments***

- Review of Concomitant Medication
- Review of Concomitant Disease
- Expired air CO breath test
- Urine collection for pregnancy (all participants with the potential to become pregnant)
- Vital signs (systolic and diastolic blood pressure, pulse rate, and respiratory rate), will be measured in sitting position after the participant has rested for at least 5 minutes.
- Weight
- Temperature
- Columbia-Suicide Severity Rating Scale (C-SSRS)
- Review of adverse events (as needed)
- Physical examination (as needed)

6.6.3 Day before Quit Day (V3) – 1 week on IMP

Six days (+ 3 days) after starting the study drug (one day prior to quit date), participants will return to the Center to complete questionnaires and assessments. Participants will also be asked to return unused IMP and will be dispensed enough IMP to last until the next scheduled visit.

The sequence of the following questionnaires and assessments will be at the discretion of the Investigator (or designee).

6.6.3.1 ***Questionnaires***

- Other Nicotine Use Questionnaire
- Modified Shiffman-Jarvik Withdrawal Scale
- Modified Cigarette Evaluation Questionnaire Extended (mCEQE)
- Minnesota Withdrawal Questionnaire

6.6.3.2 ***Assessments***

- Review of Concomitant Medication
- Review of Concomitant Disease
- Expired air CO breath test
- Urine collection for pregnancy (all participants with the potential to become pregnant)
- Vital signs (systolic and diastolic blood pressure, pulse rate, and respiratory rate), will be measured in sitting position after the participant has rested for at least 5 minutes.
- Weight
- Temperature
- Columbia-Suicide Severity Rating Scale (C-SSRS)

- Review of adverse events (as needed)
- Physical examination (as needed)

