3 INVESTIGATIONAL PLAN

3.1 OVERALL STUDY DESIGN AND PLAN

This single-group, small-scale, open-label, phase 2 study (N= 50) will evaluate centanafadine as a potential smoking cessation treatment. The dose of centanafadine SR that will be evaluated in this trial will be 400 mg TDD (200 mg BID) approximately 4 to 6 hours apart for seven weeks.

The study will consist of a 14-day screening period, a baseline visit, a 7-week treatment period, and a 7-day safety follow-up period. Participants will visit the study center a total of six times, including a screening visit (V1), baseline visit (V2), a visit one week (+ 3 days) after starting the study drug (V3), three weeks (\pm 3 days) after starting the study drug (V4), five weeks (\pm 3 days) after starting the study drug (V5), and seven weeks (\pm 3 days) after starting the study drug (V6). All participants will be requested to participate in a 7-day safety follow up period, which will consist of telephone contact seven days (+2 days) after the last dose of investigational product.

[figure not shown]

Figure 1 - Overall Study Design and Plan, 7-Week Treatment Period

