4.9.2 V3 Session Window

Participants may attend V3 up to 3 calendar days post scheduled visit.

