6.6.7 Telephone Contact

Participants will be contacted via phone on Day 1 (first day of IMP) and on weeks that they are not scheduled to visit the Center (Wk 2, Wk 4, and Wk 6) to ask how they are doing and answer any questions the participant may have.

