11.2 STATISTICAL METHODS

The estimation of the four-week continuous smoking abstinence rate at 6 weeks post target quit date is around 50% and 30% of treated individuals experiencing nausea from varenicline treatment based on the historical studies.² The smoking abstinence rate during weeks 4-7 will be calculated with 90% binomial confidence intervals, and the incidence rate of nausea will be tabulated, which will be compared with the thresholds established for efficacy and tolerability.

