5.4 Trial Visit Window

The actual assessment date is mapped into the trial week based on [Table 5.4-1](#). Trial days are derived from the formula: Trial Day = Date of assessment - Date of 1st IMP + 1. Based on the number of trial days, subjects are mapped to the corresponding trial week. In addition, only last observations within the same mapped weeks are reported in the summary tables by trial week.

Table 5.4-1 Mapped Trial Week Windows for Efficacy Analysis	
Mapped Week	Mapped Trial Day Range^{a,b}
Week 1	Day 1 - Day 7
Week 2	Day 8 - Day 14
Week 3	Day 15 - Day 21
Week 4	Day 22 - Day 28
Week 5	Day 29 - Day 35
Week 6	Day 36 - Day 42
Week 7	Day 43 - Day 49

^a Relative days to the first day of IMP.

^b Evaluations occurring more than three days after the last dosing date will be excluded from the analyses.

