8.3.6 Abstinence Rate by Week

Abstinence rate calculation:

- If subject has exhaled CO level of less than 5 ppm using the Vitalograph BreathCO monitor and there is no smoking in the self-report, then set it as abstinence.
 - Missing value check:
 - For CO value, value can be missing.
 - For self-report value, only one missing in every visit week (7 days) is allowed.

Protocol 405-201-00055 Statistical Analysis Plan

- All the others will be set as non-abstinent.
 - There are two or more missing in self-report every visit week (7 days)
 - Lost to follow-up/Early termination
 - Subjects with adequate data that they were smoking

A descriptive statistic will be provided with 90% binomial confidence intervals by week.

For all binomial confidence intervals, it is based on normal approximation. If the number of abstinent or the number of non-abstinent ≤ 5 , we will use the exact method.

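### Minor, descriptive tables only: the quit day follows V3 but SAP weeks run from first dose, so a V3 after Day 7 puts pre-quit smoking into Week 2

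*Protocol*

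**What the plan says.** **Quit day.** Protocol 6.6.3 is headed "Day before Quit Day (V3) – 1 week on IMP" and sets the visit at "Six days (+ 3 days) after starting the study drug (one day prior to quit date"). Protocol 4.9.2 lets it run late but not early: "Participants may attend V3 up to 3 calendar days post scheduled visit". Protocol 3.1 words the timing differently, as "a visit one week (+ 3 days) after starting the study drug (V3"), and SAP 3.1 agrees with that, calling V3 the Week 1 visit.

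**Week definition.** SAP 5.4 computes the trial day from the date of first dose and states: "Based on the number of trial days, subjects are mapped to the corresponding trial week". Table 5.4-1 gives Week 2 as Days 8 to 14. The mapping uses the actual assessment date, and only the last observation in a mapped week is reported. The quit date does not appear in it.

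**Scoring.** Under SAP 8.3.6 a participant is abstinent in a week if CO is below 5 ppm and the self-report shows no smoking. CO may be missing, and one diary entry per 7-day week may be missing. Everyone else is non-abstinent. The output is: "A descriptive statistic will be provided with 90% binomial confidence intervals by week".

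**Data in Week 2.** The daily message asks about smoking every day from V2 to V6 (protocol 6.7.2). CO is measured at every visit (protocol 6.5.10). Week 2 has no clinic visit of its own: protocol 6.6.7 plans telephone contact "on weeks that they are not scheduled to visit the Center (Wk 2, Wk 4, and Wk 6").

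**The concern.** The protocol's clock for abstinence starts on a day that moves with V3. The SAP's clock starts at first dose. When V3 is late, the participant has not yet reached the quit day during the first days of SAP Week 2. Smoking on those days breaks no stated requirement, yet the 8.3.6 rule fails the whole week because of it.

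At stake is the reading of the weekly series. If Week 2 is lowered by appointment timing, early success looks worse than it was and a later rise could be taken for recovery. The tables concerned are CT-5.1.2 (self-report and CO by week), CT-5.1.3 (self-report by week) and CT-6.2 (cigarettes per day by week).

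**Working it through.** **Inputs.** First dose is Day 1 (protocol 6.6.2). V3 is 6 to 9 days after first dose (protocol 6.6.3), or 7 to 10 days after it (protocol 3.1, SAP 3.1). The quit day is V3 + 1 (protocol 6.6.3). Trial day = date − first-dose date + 1 (SAP 5.4).

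**The plan's own figure.** Week = floor((day − 1)/7) + 1 gives Week 1 = Days 1–7, Week 2 = Days 8–14, and so on to Week 7 = Days 43–49. This is Table 5.4-1 exactly.

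**Pre-quit days in Week 2.** These are the days from Day 8 to the day before the quit day, so their number is quit day − 8. Post-quit days in Week 2 = 14 − quit day + 1.

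| V3 day | Possible under | Quit day | Pre-quit days in Week 2 | Post-quit days in Week 2 | V3 CO maps by date to |
|---|---|---|---|---|---|
| 7 | six days | 8 | 0 | 7 | Week 1 |
| 8 | both | 9 | 1 | 6 | Week 2 |
| 9 | both | 10 | 2 | 5 | Week 2 |
| 10 | both | 11 | 3 | 4 | Week 2 |
| 11 | one week | 12 | 4 | 3 | Week 2 |

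Under the six-days wording an on-time V3 causes no problem. Under the one-week wording even an on-time V3 (Day 8) does.

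**CO in Week 2.** V4 is three weeks ± 3 days after first dose, so no earlier than Day 18, which is Week 3. A V3 reading mapped to Week 2 is therefore the only scheduled CO there, and the last-observation rule cannot replace it. Participants entered with CO of at least 10 ppm, so a pre-quit value below 5 ppm is not to be expected as a rule.

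**Primary window.** Weeks 4 to 7 are Days 22 to 49. The latest quit day is Day 11 (six days) or Day 12 (one week), and 22 − 11 = 11 and 22 − 12 = 10. No pre-quit day enters.

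**Size for abstinence.** The documents give neither the share s of participants with V3 on Day 8 or later nor how many of them smoke before quitting. Assume that all of them do and that a late V3 is unrelated to outcome. Then reported Week 2 rate = true rate × (1 − s):

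| True rate | s = 10% | s = 25% | s = 50% | s = 100% |
|---|---|---|---|---|
| 50% | 45% | 37.5% | 25% | 0% |
| 30% | 27% | 22.5% | 15% | 0% |

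If only a fraction h of late-V3 participants smoke before quitting, the factor becomes 1 − s × h.

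**Size for cigarettes per day.** Assume a participant smokes 10 per day (the entry minimum) until quitting and none afterwards. The Week 2 mean is 10 × pre-quit days / 7: 10/7 = 1.4, 20/7 = 2.9 and 30/7 = 4.3 for V3 on Day 8, 9 and 10, although smoking stopped completely on the quit day.

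**The case against.** **It decides nothing in the trial.** Abstinence by week is one of the other efficacy endpoints, with no test or threshold attached. This stands, and it sets the grade at minor.

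**The CO part depends on the mapping.** SAP 3.1 labels V3 the Week 1 visit, and the SAP's four-week CO rules refer to scheduled visits. Strict date mapping would also push a V6 held exactly seven weeks after first dose to Day 1 + 49 = Day 50, beyond Table 5.4-1, which favours reading by label. This stands in part. SAP 8.3.6 does not say scheduled, and 5.4 says actual date. If the label governs, the V3 CO stays in Week 1 and only the diary part remains.

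**Weeks on drug is a legitimate scale.** Table 5.4-1 is openly relative to first dose and never calls Week 2 the first week after quitting. True, but the table reports abstinence, and the 8.3.6 rule then fails people for days before they were due to quit. Protocol 11.3.1 counts abstinence from the preceding session and would largely avoid this at V4, but the SAP's by-week rule does not use it.

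**Two premises are inferences.** No text expressly allows smoking before the quit day; the protocol sets a quit day and states no earlier requirement. That the quit day moves with V3 is the plain reading of 6.6.3, though that section might describe only the nominal schedule, and the design figures could not be read. If the quit day were fixed, a late V3 would no longer be the day before it, and the text would still need reconciling.

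**Stronger readings that do not hold.** A reader might infer that the comparison with the varenicline benchmark, stated for the "four-week continuous smoking abstinence rate at 6 weeks post target quit date", is disturbed. It is not: the primary window contains no pre-quit day, and a shift of a few days since quitting is immaterial beside a 50% benchmark rounded up from 44% plus about 5%. A reader might also infer that weekly CO summaries are affected, but SAP 8.3.9 and the titles of CT-6.1.1 and CT-6.1.2 do not say by week. Finally, three of four permitted V3 days is a count of calendar days, not of participants.

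**Conclusion.** The concern holds as a minor point about descriptive analyses. For any V3 after Day 7, the rules as written place pre-quit diary days in Week 2: 1 to 3 days for late visits under protocol 6.6.3, or 1 to 4 days for every participant under protocol 3.1 and SAP 3.1. Under actual-date mapping the pre-quit V3 CO goes there too.

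The direction is known for CT-5.1.2 and, if the 8.3.6 diary rule is applied to it, for CT-5.1.3: Week 2 abstinence is understated. In CT-6.2 the Week 2 average mixes two periods. The amount cannot be fixed from the documents, because it depends on the share of late V3 visits and on smoking before the quit day. The percentages above are a range under stated assumptions, not estimates.

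The primary Week 4 to 7 endpoint, its three sensitivity analyses and the nausea endpoint are not affected.

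**What to change.** In SAP 5.4 and 8.3.6:

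- Derive the quit date as the V3 date + 1. If V3 is missed, use the nominal quit day of the reconciled schedule.
- Assign the V3 CO and all diary days up to and including V3 to a pre-quit period, whatever the trial day.
- Then choose one of two layouts and apply it to CT-5.1.2, CT-5.1.3 and CT-6.2. Either report by 7-day week since the quit date (first week Days 8–14, 9–15, 10–16 or 11–17 for V3 on Day 7, 8, 9 or 10), or keep the Table 5.4-1 weeks, start the Week 2 diary check on the quit date and apply the one-missing allowance to the days that remain.
- Keep Days 22 to 49 for the primary endpoint.

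Separately, reconcile the six-days timing in protocol 6.6.3 with the one-week timing in protocol 3.1 and SAP 3.1, since this determines whether some or all participants are affected.

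The cost is SAP wording and one date derived from a recorded visit; no new data are needed. The downside is a Week 2 of 4 to 6 diary days for V3 on Days 8 to 10 (3 days for V3 on Day 11) or, with weeks since quitting, an incomplete last week for the same participants if the series stops at Day 49.

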6.6.4 Visit 4 (V4) – 3 weeks on IMP

Three weeks (\pm 3 days) after starting the study drug, participants will return to the Center for V4 to complete questionnaires and assessments. Participants will also be asked to return unused IMP and will be dispensed enough IMP to last until the next scheduled visit.

The sequence of the following questionnaires and assessments will be at the discretion of the Investigator (or designee).

6.6.4.1 *Questionnaires*

- Other Nicotine Use Questionnaire
- Modified Shiffman-Jarvik Withdrawal Scale
- Modified Cigarette Evaluation Questionnaire Extended (mCEQE)
- Minnesota Withdrawal Questionnaire

6.6.4.2 *Assessments*

- Review of Concomitant Medication
- Review of Concomitant Disease
- Expired air CO breath test
- Urine collection for drug screen and pregnancy (all participants with the potential to become pregnant)
- Blood collection for safety laboratory testing, pharmacokinetics, and future biospecimen research (for those participants who consented to this optional collection)
- Vital signs (systolic and diastolic blood pressure, pulse rate, and respiratory rate), will be measured in sitting position after the participant has rested for at least 5 minutes.
- Weight
- Temperature
- Columbia-Suicide Severity Rating Scale (C-SSRS)
- Review of adverse events (as needed)
- Physical examination (as needed)

6.6.5 Visit 5 (V5) – 5 weeks on IMP

Five weeks (\pm 3 days) after starting the study drug, participants will return to the Center for V5 to complete questionnaires and assessments. Participants will also be asked to return unused IMP and will be dispensed enough IMP to last until the next scheduled visit.

The sequence of the following questionnaires and assessments will be at the discretion of the Investigator (or designee).

6.6.5.1 *Questionnaires*

- Other Nicotine Use Questionnaire
- Modified Shiffman-Jarvik Withdrawal Scale
- Modified Cigarette Evaluation Questionnaire Extended (mCEQE)
- Minnesota Withdrawal Questionnaire

6.6.5.2 **Assessments**

- Review of Concomitant Medication
- Review of Concomitant Disease
- Expired air CO breath test
- Urine collection for drug screen and pregnancy (all participants with the potential to become pregnant)
- Vital signs (systolic and diastolic blood pressure, pulse rate, and respiratory rate), will be measured in sitting position after the participant has rested for at least 5 minutes.
- Weight
- Temperature
- Columbia-Suicide Severity Rating Scale (C-SSRS)
- Review of adverse events (as needed)
- Physical examination (as needed)

6.6.6 Final Study Visit (V6) – 7 weeks on IMP

Seven weeks (\pm 3 days) after starting the study drug, participants will return to the Center for V6 to complete questionnaires and assessments. Participants will also be asked to return all unused IMP.

The sequence of the following questionnaires and assessments will be at the discretion of the Investigator (or designee).

6.6.6.1 **Questionnaires**

- Other Nicotine Use Questionnaire
- Modified Shiffman-Jarvik Withdrawal Scale
- Modified Cigarette Evaluation Questionnaire Extended (mCEQE)
- Minnesota Withdrawal Questionnaire
- Fagerström Test for Nicotine Dependence

6.6.6.2 **Assessments**

- Review of Concomitant Medication
- Review of Concomitant Disease
- Expired air CO breath test
- Alcohol breath test
- Urine collection for urinalysis and pregnancy (all participants with the potential to become pregnant)
- Blood collection for safety laboratory testing, pharmacokinetics, and future biospecimen research (for those participants who consented to this optional collection)
- Vital signs (systolic and diastolic blood pressure, pulse rate, and respiratory rate), will be measured in sitting position after the participant has rested for at least 5 minutes.
- Weight
- Temperature
- Electrocardiogram (ECG) -- A standard 12-lead ECG will be recorded after the participant has rested for at least 5 minutes in a supine position.
- Columbia-Suicide Severity Rating Scale (C-SSRS)
- Review of adverse events (as needed)

- Physical examination (as needed)

